**Changes to original registration:**

**Primary outcome measure:** the primary outcome measure was changed from ongoing pregnancy (i.e., clinical pregnancy at  $>14$  weeks of gestation) to the preferred outcome of live birth (LB, a delivery at  $>20$  weeks, with a live infant).

The AFC cut-off was changed to  $\geq 5$  (changed from  $\geq 10$ ) to be in line with the definition of decreased ovarian reserve and increase the eligible population.

**Trial registration:** ClinicalTrials.gov ID: NCT03095053

Protocol submission: 23 March 2017

Protocol revised submission: 28 March 2017

Randomized Controlled Trial registered and posted: 29 March 2017

Data collection start: 21 February 2018

Data collection was commenced at  $>20$  weeks from the date of last patient randomized had undergone FET

Data analysis start: 25 April 2018

## **Description**

### **Brief description**

#### Introduction

Embryo aneuploidy is likely the leading cause of implantation failure in IVF cycles. Since the inception of IVF, non-invasive morphology based scoring has been the most widely used embryo selection method, resulting in relatively low embryo implantation rates. Our understanding of the optimal conditions required for *in vitro* embryo culture in IVF has advanced significantly over the past two decades. The implementation of improved *in vitro* embryo culture technologies (i.e., culture media and incubators) has resulted in an increase in the number of good quality embryos and consequently in increased numbers of blastocysts. While blastocyst transfers have seemingly improved the reproductive outcomes of IVF, they still remain suboptimal. The main objective of this randomized controlled trial (RCT) will be to investigate whether preimplantation genetic testing (i.e., PGT with comprehensive chromosome screening (CCS)) for aneuploidy is a superior embryo selection method, with the live birth outcomes of euploid blastocyst frozen embryo transfers (FET) compared with the LB outcomes of unknown-ploidy blastocyst FET, with blastocysts selected on (standard) morphological score.

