#### Methods

This RCT will be conducted at a single private IVF centre performing routine segmented-IVF, with intracytoplasmic sperm injection (ICSI), blastocyst freeze-all, and artificial frozen embryo transfer (art-FET). Normo-ovulatory infertile patients, with maternal age  $\leq 35$  years and at least two blastocysts with a morphology score of 2BB cryopreserved, will be randomized by computer-generated randomized allocation to either the PGT or morphology arm of the trial. All transfers will be single embryo transfers (SET), with only the first FET cycles following freeze-all to be analyzed.

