## Objectives

The primary objective of this RCT will be to investigate whether PGT for aneuploidy as a blastocyst selection method is superior to standard morphology scoring blastocyst selection, comparing the reproductive outcomes in FET cycles. The decision to transfer all blastocysts in FET will eliminate any potential impact of ovarian stimulation confounding on endometrial receptivity and to use freeze-all cycles will allow the use of the primary blastocysts of blastocyst cohorts. The primary outcome measure of this trial will be LB, with a LB defined as a pregnancy cycle delivering at >20 weeks of gestation.

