## Secondary objectives

The secondary objective of the RCT will be to investigate whether euploid blastocyst transfer results in reduced miscarriage, with a miscarriage defined as a clinical pregnancy lost at <20 weeks of gestation.

**Keywords:** blastocyst; comprehensive chromosome screening; euploidy; frozen embryo transfer

**Funding:** This RCT will not receive any specific grant from funding agencies in the public, commercial, or not-for-profit sectors, and therefore will be wholly funded by centre running the trial.

**Declaration of Interests:** The authors declare no conflicts of interest.

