## **Materials and methods**

### **Study design**

The RCT will be performed as a single private IVF center trial. The patient population of the trial will include young patients undergoing autologous blastocyst freeze-all IVF cycles from March 2017. In this trial, a patient will undergo a blastocyst-freeze-all cycle after ICSI and only the reproductive outcomes of the first FET following the freeze-all will be analyzed. Currently at the trial centre more than 95% of cycles are extended culture cycles and more than 80% of these cycles result in freeze-all cycles, with a live birth rate after the first FET of >45% per oocyte retrieval.

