## **Randomisation**

Patient couples who satisfy the inclusion criteria and who completed an informed consent will randomized by computer generated number in a 1:1 ratio on day 5 of in vitro embryo culture to the two arms, with the FET drug prescription indicating allocation to the ***the PGT group***, in which all blastocysts will be assessed according to standard morphological parameters, with the best scoring blastocyst to undergo biopsy and PGT for aneuploidy or ***the morphology group***, in which all blastocysts will be assessed according to standard morphological parameters, with the best scoring blastocyst selected for transfer (figure 1). Patient couples in the PGT group will be subgrouped

according to whether the blastocyst biopsied is predicted to be euploid (**the euploid subgroup**) or aneuploid (**the aneuploid subgroup**). In the aneuploid group the next best morphology scoring blastocyst will be transferred.

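### Couples are randomised to PGT or morphology, but the Brief description compares euploid with unknown-ploidy transfers, and Statistics names neither the primary contrast nor the analysis set

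*Combined protocol and SAP*

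**What the plan says.** **Allocation.** Methods in the Brief description says that patients "will be randomized by computer-generated randomized allocation to either the PGT or morphology arm of the trial". Randomisation gives a 1:1 ratio on day 5 of culture. It adds that "Patient couples in the PGT group will be subgrouped" as euploid or aneuploid by the biopsy result, and that after an aneuploid result the next blastocyst in morphology order is transferred. Under that section and Figure 1 a single blastocyst per PGT couple is tested, so the replacement is of unknown ploidy.

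**Primary question.** Objectives asks whether "PGT for aneuploidy as a blastocyst selection method is superior to standard morphology scoring blastocyst selection". The main-objective sentence in the Brief description (Introduction) begins in the same way, asking whether PGT "for aneuploidy is a superior embryo selection method", but then continues "with the live birth outcomes of euploid blastocyst frozen embryo transfers (FET) compared with the LB outcomes of unknown-ploidy blastocyst FET".

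**Other places.** Secondary objectives will "investigate whether euploid blastocyst transfer results in reduced miscarriage" and gives no comparator. Sample size calculation takes 66% from euploid transfers and 52% from morphology-selected transfers, then sizes for a 20-point difference without saying between which groups. Statistics lists chi-square or Fisher's exact tests and risk ratios, but no groups and no analysis set. Study design says that "only the reproductive outcomes of the first FET following the freeze-all will be analyzed". That fixes the cycle, not which randomised couples are counted.

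**The concern.** The document holds two different primary contrasts. One compares everyone allocated to PGT with everyone allocated to morphology, and randomisation protects it. The other compares those PGT couples whose best-scoring blastocyst tested euploid with transfers of unknown ploidy.

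The second contrast has two faults. First, it selects on one side only. PGT couples whose best blastocyst tests aneuploid leave the PGT side, while comparable couples in the morphology arm stay in because they were never tested. Second, it does not define its own comparator. The aneuploid subgroup also receives a blastocyst of unknown ploidy chosen by morphology, so the wording could exclude those couples or pool them with the morphology group.

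Either way, the result no longer answers the question in Objectives, because using PGT as a strategy includes what happens after an aneuploid result. With three outcome groups and no named test, the contrast could also be settled after results are known.

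**Working it through.** The inconsistency rests on the text alone. The arithmetic below only shows how far apart the two contrasts can lie.

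**Inputs from Sample size calculation:** 66% (euploid transfers), 52% (morphology), a 20-point difference, 80% power, significance level 0.05, n = 74. The rates are for ongoing pregnancy and stand in here for live birth.

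**Assumptions not in the documents:** euploid share *f* of 50%, 60% or 70%; next-best blastocyst rate *q* = 52%; 74 randomised per arm; two-sided 5%. The 20-point difference is taken as euploid 72% against morphology 52%, although the plan does not assign it to that pair.

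**The plan's figure.** The pooled two-proportion formula is n per arm = [z(α)·√(2p̄(1−p̄)) + z(0.80)·√(p₁(1−p₁) + p₂(1−p₂))]² / (p₂−p₁)². With a one-sided 0.05 level it gives 72 (52% vs 72%), 74 (50% vs 70%) and 76 (46% vs 66%). Two-sided, the first and last become 92 and 96. So 74 reproduces as a per-arm, one-sided figure for 20 points. No two-arm variant tried gave 74 as a total.

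**Dilution.** With p_E the euploid rate, the PGT-arm rate is f·p_E + (1−f)·q. The difference between arms is therefore the euploid difference minus (1−f)(p_E − q). The euploid contrast overstates the arm effect whenever the next-best blastocyst does worse than a euploid one.

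**Power** is Φ[(d − 1.96·s₀)/s₁], where d is the difference, s₀ the pooled standard error and s₁ the unpooled one. For *f* = 60% and 72% vs 52%:

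- Between arms (74 vs 74): PGT rate 0.6×0.72 + 0.4×0.52 = 0.64, d = 0.12, s₀ = 0.0811, s₁ = 0.0805. (0.12 − 0.1590)/0.0805 = −0.485, so power is 31%.
- Euploid vs morphology (44 vs 74): d = 0.20, s₀ = 0.0935, s₁ = 0.0892. (0.20 − 0.1832)/0.0892 = 0.188, so power is 57%.

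| Euploid rate | *f* | Euploid couples | Power, euploid contrast | Arm difference (points) | Power, between arms |
|---|---|---|---|---|---|
| 72% | 50% | 37 | 52% | 10 | 23% |
| 72% | 60% | 44 | 57% | 12 | 31% |
| 72% | 70% | 52 | 62% | 14 | 41% |
| 66% | 50% | 37 | 28% | 7.0 | 13% |
| 66% | 60% | 44 | 31% | 8.4 | 18% |
| 66% | 70% | 52 | 34% | 9.8 | 22% |

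One-sided, power between arms in the 72% case is 34–53%.

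**Precision between arms.** The 95% CI half-width is 1.96·s₁. Over the six rows it is 15.7 to 16.0 points at 74 per arm.

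**The case against.** The best defence is that the plan already points to the arms. Objectives, Methods and Randomisation all work at that level, euploid and aneuploid are called subgroups, and the conflicting words are a trailing clause in a summary. Secondary objectives names no comparator, so it contradicts nothing by itself. Figure 1, as far as its layout can be read, follows the aneuploid subgroup to live birth.

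Much of this stands, and it limits the point. A reader might infer that the sponsor has committed to dropping the aneuploid couples, or chose the contrast after seeing results. The documents support neither: they contain both readings and do not choose between them. The defence does not remove the conflict, because the clause is part of the main-objective sentence and Statistics, where the matter should be settled, is silent.

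A reader might also compare the 71% two-sided power for 72% vs 52% with the 23–41% between arms and attribute the whole fall to the contrast. That is not like for like, since 71% requires 74 euploid couples and only 37–52 would exist under the assumed shares. The one-sided basis that reproduces 74, and the gap between 66 − 52 = 14 points and the 20 points planned for, are separate matters.

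**Conclusion.** The point holds and should be fixed before the result is interpreted. The text supplied states two incompatible primary contrasts, and the one in the Brief description is split by a post-randomisation result. Nothing supplied resolves this or says how a randomised couple without a transfer is counted. Two parts of the document were not available, so absence is asserted only for the text supplied.

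On the assumptions above, the euploid contrast would exceed the arm-level difference by 6–10 points if the euploid effect is 20 points (20 − 14 to 20 − 10), and by 4.2–7.0 points if it is 14 (14 − 9.8 to 14 − 7.0). The euploid share, the next-best rate and the use of 20 points for this contrast are assumptions, so these sizes are illustrative. The conflict in the text does not depend on them.

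**What to change.** - **Statistics:** state that the primary analysis compares live birth per randomised couple, all PGT-arm couples (euploid plus aneuploid subgroups) against all morphology-arm couples. Count a couple without a transfer as no live birth, and report the risk ratio with its 95% CI.
- **Contrasts by PGT result:** label these as non-randomised and descriptive, for miscarriage as well as live birth.
- **Brief description and Secondary objectives:** reword both to match Objectives.
- **Sample size calculation:** say that 66% is a euploid-transfer rate, not a rate expected for the whole PGT arm.
- **Timing:** date the clarification. The registration changes list "Data analysis start: 25 April 2018". If the rule was written after that, disclose it as a later clarification and do not call it prespecified.

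This needs wording only and no new data. The cost is a smaller expected difference between arms, with a 95% CI of about ±16 points at 74 per arm. That is wider than the 7–14 points illustrated, and the report will have to show the imprecision.

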#### Methods

This RCT will be conducted at a single private IVF centre performing routine segmented-IVF, with intracytoplasmic sperm injection (ICSI), blastocyst freeze-all, and artificial frozen embryo transfer (art-FET). Normo-ovulatory infertile patients, with maternal age  $\leq 35$  years and at least two blastocysts with a morphology score of 2BB cryopreserved, will be randomized by computer-generated randomized allocation to either the PGT or morphology arm of the trial. All transfers will be single embryo transfers (SET), with only the first FET cycles following freeze-all to be analyzed.

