## **Biopsy**

Blastocysts with morphological grades of  $\geq 2$ BB will be biopsied on day 5 of in vitro embryo culture. Biopsies will be performed using a Hamilton Thorne Zilos laser (Hamilton Thorne, MA, USA), with 3-10 trophectoderm cells removed from the blastocysts.

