## **Blastocyst cryopreservation**

Vitrification and warming of blastocysts will be performed using ultra-rapid technologies (Cryotop, Kitazato BioPharma Co. Ltd, Fuji-city, Japan), according to the manufacturer's guidelines. Blastocysts were warmed and transferred on the same day; after warming the blastocysts were placed in incubation for approximately 2 hours and then morphologically reassessed.

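### The analysis is tied to first FET cycles although couples are randomised earlier, and no rule keeps a randomised couple without an FET in the denominator

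*Combined protocol and SAP*

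**What the plan says.** The analysed unit is stated twice. The brief description (Methods) says "with only the first FET cycles following freeze-all to be analyzed". Study design says "only the reproductive outcomes of the first FET following the freeze-all will be analyzed".

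The Randomisation section allocates couples "in a 1:1 ratio on day 5 of in vitro embryo culture". Biopsy says that usable blastocysts "will be biopsied on day 5 of in vitro embryo culture", and Figure 1 places biopsy and cryopreservation after randomisation. Sequencing, warming and transfer come later still. Blastocyst cryopreservation adds that "after warming the blastocysts were placed in incubation for approximately 2 hours and then morphologically reassessed".

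The brief Methods orders events differently. There, patients with "at least two blastocysts with a morphology score of 2BB cryopreserved, will be randomized by computer-generated randomized allocation", so freezing is a condition of entry. The Eligibility criteria instead rest on the day-5 count of usable blastocysts.

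No section defines an intention-to-treat population, gives the denominator for live birth, or says how to handle a randomised couple without an FET. Outcome measures defines live birth at the level of a pregnancy cycle. Statistics lists tests only. The sample size calculation has no allowance for attrition. The timing of data collection (Data section) takes for granted that the last randomised couple had an FET.

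**The concern.** A first FET exists only if several steps after allocation succeed. If the FET cycle is the unit, whether a couple is analysed depends on events after randomisation. Those events need not be alike in the two arms: trophectoderm biopsy and sequencing are done only in the PGT arm. The Randomisation section sorts PGT couples "according to whether the blastocyst biopsied is predicted to be euploid" or aneuploid, and names no branch for a failed biopsy or a test without a result.

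The trial asks whether one selection method is superior to another. If a method costs some couples their transfer, that cost belongs in its result. Dropping those couples removes failures from one denominator, and randomisation no longer protects the comparison of live-birth rates. This would affect a comparison of the two whole arms. It is separate from the question of how the euploid and aneuploid subgroups are handled.

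**Working it through.** **1. Order of events.** Day-5 count of usable blastocysts, then randomisation, biopsy (PGT arm only), vitrification, sequencing result (PGT arm only), warming, FET. Every step after randomisation can stop a couple from contributing a first FET.

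**2. Inputs.**
- 74 couples per arm, from the sample size calculation. The text does not say whether 74 is per arm or in total. It is reproduced as a per-arm figure with a one-sided 0.05 level, 80% power and 50% v 70%: [1.645·√(2·0.6·0.4) + 0.842·√(0.25 + 0.21)]² / 0.20² = 73.1, rounded up to 74. I therefore take it as per arm.
- 52% success, the centre's ongoing pregnancy rate with morphology selection (same section). Using it as a live-birth rate per randomised couple is an assumption.
- d, the number of couples without an FET. The documents give no figure, so d is varied.

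**3. Effect on the rate.** Rate per FET = rate per randomised couple × 74 / (74 − d). With 0.52 × 74 = 38.48 expected live births:

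| d in one arm | Rate per FET | Apparent gain |
|---|---|---|
| 0 | 52.0% | 0 |
| 2 | 38.48/72 = 53.4% | 1.4 points |
| 4 | 38.48/70 = 55.0% | 3.0 points |
| 8 | 38.48/66 = 58.3% | 6.3 points |

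**4. Effect on the test.** Live births in each arm are drawn from a binomial(74, 0.52). The affected denominator is cut to 74 − d, and the arms are compared by an uncorrected chi-square test. The table gives the probability of a significant result favouring PGT (z > 1.96, nominal 2.5%), by full enumeration.

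| PGT couples without FET | Morphology couples without FET | P(false result favouring PGT) |
|---|---|---|
| 0 | 0 | 2.9% |
| 2 | 0 | 4.2% |
| 4 | 0 | 6.0% |
| 8 | 0 | 12.4% |
| 4 | 4 | 2.9% |
| 8 | 8 | 3.3% |

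By symmetry, four losses in the morphology arm alone give a 6.0% chance of a false result favouring morphology.

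**5. Sensitivity to the null.** The first four rows hold the rate per randomised couple equal. If success per FET is 52% in both arms instead, the probability of a result favouring PGT is 2.7% at d = 4 and 2.6% at d = 8 (PGT losses only), so there is no inflation. The two nulls answer different questions. For a superiority claim about a selection strategy, the one per randomised couple is relevant.

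**The case against.** The first-FET wording most naturally excludes second and later transfers. Neither sentence says that couples without an FET are dropped, and Study design itself quotes a centre live-birth rate per oocyte retrieval, which is a wider denominator. This stands in part: the loss of couples follows from a missing rule and is not an explicit exclusion. But the stated unit is still the FET cycle, and nothing brings a couple without one back in.

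A reader might go further and infer that several exits exist only in the PGT arm, so that the result must be tilted toward PGT. The documents do not support that. Each couple enters with at least two usable blastocysts, and one is biopsied. An aneuploid result still leads to a transfer, of the next-ranked blastocyst. Failed warming or a cancelled FET can occur in either arm. The plan is silent on a failed biopsy or a test without a result, but silence does not show that the couple leaves. What remains is that biopsy and sequencing are confined to one arm, so unequal loss is possible.

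A reader might also take the brief Methods to count couples by frozen blastocysts. It does not: "cryopreserved, will be randomized by computer-generated randomized allocation" gives freezing as an entry condition. Read literally, this puts freezing before allocation, so loss before freezing could not be a post-randomisation exit. The defect there is a conflict of timing with Randomisation and Figure 1.

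Finally, the inflation figures rest on assumed one-sided losses and on the null chosen. That is correct, and they are an illustration only.

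**Conclusion.** The point holds as a gap in the analysis plan. The stated unit permits exclusions after randomisation, and no rule prevents them. The documents give no loss rate in either arm, so neither the size nor the direction of any bias can be derived, and bias toward PGT is not established.

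Under the stated assumptions (74 per arm, 52% per randomised couple in both arms, losses in the PGT arm only), four losses roughly double the chance of a false superiority result, from 2.9% to 6.0%, and eight take it to 12.4%. With equal losses it stays at 2.9% to 3.3%. A handful of couples lost unevenly would therefore matter in a trial of this size, which is reason enough to fix the denominator. The timing conflict between the brief Methods and the Randomisation section is a firm but smaller finding.

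**What to change.** In the brief Methods and in Study design, replace the first-FET-only wording with a statement that every randomised couple is analysed and that the outcome is taken from the first FET, later transfers not counting. Add to Statistics:

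> *The primary analysis includes every randomised couple in the allocated arm. The outcome is live birth from the first FET; a couple with no FET for any reason counts as no live birth. The per-FET rate is supportive, and reasons for no FET are reported by arm.*

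This keeps the exclusion of later transfers. Reconcile the brief Methods with Eligibility criteria, Exclusion criteria and Randomisation, so that eligibility rests on information available before allocation.

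The cost is mainly wording. The analysis needs a record of allocation for every randomised couple. The plan describes no allocation list: it says that the FET drug prescription shows the arm and that data come from the centre's IVF database. It should be confirmed that couples who never reached an FET can be identified by arm. The downside is that the reported live-birth rates may be slightly lower.

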#### Consent and Ethics

Akdeniz University Medical Faculty Clinical Research Ethics Committee has approved the trial (reference number: 2015/399), with anonymized results to be released in ClinicalTrials.gov. All patients will provide informed consent, which included an agreement for the use of anonymised data for research and SET.

